6.3 Lifestyle Restrictions

In addition to the eligibility criteria at screening (Sections 6.1 and 6.2), participants are required to adhere to the following restrictions during the study. The lifestyle restrictions listed below are not exclusion criteria; if noncompliance occurs, following discussion between the investigator and medical monitor, a protocol deviation will be completed and the participant will be allowed to participate in the study.

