6.2 Exclusion Criteria

Participants are excluded from the study if any of the following criteria apply:

5) Medical Conditions

- a) History of gastrointestinal (GI) disease: gastroesophageal reflux, dyspepsia, protracted nausea, chronic diarrhea, upper GI ulcer disease within 6 months, ulcerative colitis, regional enteritis, diverticulosis, diverticulitis, or surgery that could affect the absorption of study drug
- b) History of upper or lower GI bleeding within 6 months, including hemorrhoids with rectal bleeding
- c) Any gastrointestinal surgery that could affect the absorption of study intervention
- d) Clinically relevant head injury within the last 2 years, as judged by the investigator
- e) Any intracranial bleeding or history of intracranial bleeding
- f) Intracranial tumor or aneurysm or abdominal aneurysm

- g) Major surgical procedures within 4 weeks prior to dosing) or planned within 2 weeks after completion of the study
- h) History or evidence of abnormal bleeding or coagulation disorder and/or evidence of coagulopathy, prolonged or unexplained clinically significant bleeding, or frequent unexplained bruising or thrombus formation, or a history of spontaneous bleeding, such as epistaxis, or family history of coagulopathies
- i) History of menorrhagia
- j) Inability or not willing to be venipunctured/cannulated and/or tolerate venous access
- k) Any history of drug or alcohol abuse as defined in Diagnostic and Statistical Manual of Mental Disorders (5th Edition) (DSM 5), Diagnostic Criteria for Drug and Alcohol Abuse
- a) Regular alcohol consumption in males > 21 units per week and females > 14 units per week (1 unit = ½ pint beer, or a 25 mL shot of 40% spirit, 1.5 to 2 units = 125 mL glass of wine, depending on type)
- b) Current smokers and those who have smoked (or used other nicotine-containing products or devices) within the last 12 months. A positive urine cotinine result at screening or admission
- 1) Any acute or chronic medical illness considered clinically significant by the investigator
- m) Donation of blood to a blood bank or in a clinical study (except a screening visit) within 4 weeks of study enrollment (within 2 weeks for plasma only)
- n) Blood transfusion within 4 weeks of study enrollment
- o) Evidence of current SARS-CoV-2 infection

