6.3.3 Caffeine. Alcohol and Tobacco

- During the study, participants will abstain from ingesting caffeine- or xanthine-containing products (eg, coffee, tea, cola drinks, and chocolate) for 24 hours prior to admission until discharge from the study.
- During the study, participants will abstain from alcohol for 24 hours prior to screening and the 24 hours prior to admission until discharge from the study.
- Participants are not permitted to smoke or use electronic cigarettes or any nicotine-containing products within 12 months prior to screening until discharge from the study.

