6.3.4 Activity

- Participants are to refrain from strenuous exercise and contact sports from at least 72 hours before the screening visit and then from 72 hours prior to admission until discharge from the study.
- Must not donate blood or plasma (outside of this study), within 4 weeks of study enrollment throughout the study duration, and for at least 90 days following last dose of study medication

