6.4.2 Activity

- Participants are to refrain from strenuous exercise and contact sports from at least 72 hours before the screening visit and then from 72 hours prior to admission until discharge from the study.
- Must not donate blood or plasma (outside of this study), from screening throughout the study duration, and for at least 90 days following last dose of study medication

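### Does Section 6.3 let in recent nicotine users and blood donors whom Section 6.2 excludes?

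*Combined protocol and SAP*

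**What the plan says.** Section 6.3 introduces a set of diet, caffeine, alcohol, tobacco and activity rules as additional to the eligibility criteria in Sections 6.1 and 6.2, to be kept while the study runs. It then states: "The lifestyle restrictions listed below are not exclusion criteria". If a rule is broken, the investigator and the medical monitor discuss it, after which "a protocol deviation will be completed and the participant will be allowed to participate in the study".

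Two of those rules look back to a time before entry and share a subject with Section 6.2.

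- Nicotine. Section 6.2 excludes "Current smokers and those who have smoked (or used other nicotine-containing products or devices) within the last 12 months". It adds: "A positive urine cotinine result at screening or admission". Section 6.3.3 says participants are "not permitted to smoke or use electronic cigarettes or any nicotine-containing products within 12 months prior to screening".
- Donation. Section 6.2, criterion 5)m), excludes blood donors "within 4 weeks of study enrollment (within 2 weeks for plasma only". Section 6.3.4 says: "Must not donate blood or plasma (outside of this study), within 4 weeks of study enrollment throughout the study duration". Section 6.4.2, a second section headed Activity, has: "Must not donate blood or plasma (outside of this study), from screening throughout the study duration".

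Table 2-1 treats a person as enrolled once consent is signed.

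**The concern.** The statement that these rules are not exclusion criteria covers the whole list, with no exception for items that also stand in Section 6.2. The promise that the person may take part is worded as an entry decision. The look-back windows can only be breached before entry, so reading Section 6.3 as covering on-study lapses alone leaves those words with nothing to do.

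Taken literally, someone who used nicotine 10 months before screening, or gave blood 3 weeks before consent, fails Section 6.2 but is accepted with a deviation under Section 6.3. Two staff members could decide the same case in opposite ways. One person would count either as a screen failure or as one of the 16 randomized. The donation rule also matters in practice, because the study itself may draw up to 550 mL of blood (Section 9).

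A smaller question is whether Section 6.3 lets a participant who breaks the fasting or meal rule be dosed in that period, which could blur the fed-versus-fasted comparison.

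**Working it through.** The main question is settled by reading the passages together.

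**Which text decides who enters**

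| Place | What it does |
|---|---|
| Section 6 | Bars prior approval of deviations from enrollment criteria |
| Section 6.2 | Any one criterion excludes; its closing text requires every criterion to be met in full |
| Section 6.3 | Adds restrictions to 6.1 and 6.2; says the added list is not itself exclusionary |
| Section 7.2 | Only people who meet the inclusion criteria and no exclusion criterion may be randomized |
| Section 9 | Screening must confirm all eligibility criteria before randomization; no waivers |
| Table 2-1 | Drug-screen results, cotinine included, are reviewed before dosing |

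**Three test cases**

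1. Nicotine 10 months before screening. This meets a Section 6.2 exclusion, so Section 7.2 bars randomization. Section 6.3 cannot rescue the person, since that would be the kind of waiver that Sections 6 and 9 forbid.
2. Blood donated 3 weeks before consent. This meets criterion 5)m), with the same result.
3. Plasma donated 3 weeks before consent. This is outside the 2-week window in 5)m), so the person is eligible. It is inside the 4 weeks of 6.3.4, so a deviation is recorded and the person takes part. It is before the start point in 6.4.2, so there is no breach there. Sections 6.2 and 6.3.4 work together here; the mismatch is between 6.3.4 and 6.4.2, and it affects only whether a deviation is logged.

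**Could numbers be affected?** Inputs from Section 10.2: 13 evaluable participants, intra-subject CV 28.3%, 90% CI within 80% to 125% of the point estimate.

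- σ = √ln(1 + 0.283²) = 0.2776.
- Precision probability = P(t(0.95, df) · s · √(2/n) ≤ ln 1.25), where s² follows σ²χ²(df)/df.
- Paired, df = n − 1: at n = 13 this gives 80.3%, which reproduces the plan's 80%. At n = 12 it gives 72.1%.
- Pooled over the four randomized periods, df = 4n − 1 − (n − 1) − 3 − 3 = 3n − 6: 95.9% at n = 13 and 90.2% at n = 12.

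To reach 12 evaluable, the study must lose 16 − 12 = 4 participants without replacing any. At least one of them would have to be an ineligible person who was admitted against Section 7.2 and later removed. Section 10.3 has no eligibility condition in either PK set that would remove such a person, and Section 7.2 allows up to 4 replacements (maximum 20 dosed).

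**Fasting and meals.** Section 6.3.1 already makes a fully eaten meal a condition of fed dosing, meals are served and recorded on the unit, and Section 8.1 covers significant noncompliance. The documents give no food ratio R. Assume R between 1.25 and 3.0, and one profile in 13 that loses the whole contrast. The food-effect ratio then shifts by R^(−1/13) − 1, from −1.7% to −8.1%. The 90% CI at n = 13 has half-width 1.782 × 0.2776 × √(2/13) = 0.194 log units, or −17.6% to +21.4%.

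**The case for a change.** The strongest case for a change is textual. The two look-back windows match exactly for nicotine and for whole blood. Section 6.3 disclaims exclusionary force for everything below it, and it contains no sentence giving Section 6.2 precedence. Criterion 10)b) in Section 6.2 also makes inability to keep the Section 6.3 rules an exclusion, so the two sections pull against each other. A few words would cure this at almost no cost.

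Part of that stands. The overlap is real, the disclaimer is too broad, and the donation wording in Sections 6.2, 6.3.4 and 6.4.2 does not agree. But precedence does not have to be stated inside Section 6.3, because Section 7.2 states who may be randomized and Section 9 repeats the requirement. Saying that a list adds no exclusion criteria does not cancel one that stands elsewhere. Criterion 10)b) points toward keeping people out, so it gives no support to the reading that Section 6.3 lets them in.

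**Conclusion.** The concern does not hold as a fault in the plan. Sections 6, 6.2, 7.2 and 9 agree that the Section 6.2 criteria control randomization, so a recent nicotine user or blood donor is not admitted through Section 6.3. The remainder is a clerical slip: an over-broad disclaimer and three unaligned donation windows, which can be reconciled whenever the text is next revised. This review takes no position on which window is intended.

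No effect on the primary or secondary results is shown. The bioavailability and food-effect ratios are within participant, and the documents give no effect of nicotine or donation on milvexian exposure. The fall from 80.3% to 72.1% needs an unlikely chain of unreplaced losses. The shift from one misclassified meal profile rests on an assumed food ratio and stays well inside the interval width. Handling of such profiles is properly left to the SAP, which Section 10.4 assigns to settle participant selection and spurious data before database lock.

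The conclusion assumes that site staff apply Section 7.2 as written.

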6.3.1 Meals and Dietary Restrictions

- 11) Eligible participants will be admitted to the clinical facility on the morning of Day of Treatment Period and will fast overnight for a minimum of 10 hours. Participants will be confined at the study site through 72 hours (to morning of Day post final IP dose in Treatment Period. Standardized meals will be served throughout the confinement portion of the study and should be the same for every treatment period (except for the high-fat meal which is only served in 2 of the treatment periods).
- 1) Participants should fast (nothing to eat or drink except water) for at least 10 hours prior to collection of specimens for scheduled clinical laboratory tests.
- 12) Fasting Requirements:
 - a) On the evening prior to dosing the fasted regimens, participants will be provided with a light snack and will then be required to fast (nothing to eat or drink except water) from 10 hours prior to administration of study treatment. Participants must not drink water from 1 hour before until 1 hour after administration of study treatment except water provided to take study treatment. Water may be consumed ad libitum at other times. Decaffeinated fluids will be allowed ad libitum from lunch time (approximately 4 hours after study treatment administration).
 - b) On Day (dosing day), a standard lunch will be served approximately 4 hours post dose. A standard evening meal will be served approximately 10 hours post dose, and an evening snack at approximately 14 hours post dose. The percentage of food consumed and timing of meals will be recorded for all Day meals. Meals will be provided to participants at standardized times on non-dosing days.
- 13) Fed Dosing: Two regimens will be dosed in the fed state, following a high-fat breakfast.
 - a) On the evening prior to dosing the fed regimen, participants will be provided with a light snack and will fast from all food and drink (except water) for a minimum of 10 hours prior to administration of study treatment until the following morning, when they will be provided with a high-fat breakfast.
 - b) Participants must not drink water from 1 hour before until 1 hour after administration of study treatment except water provided to take study treatment and fluids given with the high-fat meal. Water may be consumed ad libitum from 1 hour after administration of study

- treatment. Decaffeinated fluids will be allowed ad libitum from lunch time (approximately 4 hours after administration of study treatment).
- c) The meal (high fat) should be consumed over a maximum period of 25 minutes, with dosing occurring 30 minutes after the start of the meal. Participants should be encouraged to eat their meal evenly over the 25-minute period. It is acknowledged that some participants will take less time to eat, but dosing should still occur 30 minutes after the start of the meal. Participants must consume 100% of the predose meal in order to be eligible for dosing.
- 14) The acceptable deviation for the predose meal from the nominal dosing time point is:
- 15) The meal will be administered \pm 5 minutes of the nominal time point
 - a) A standardized lunch will be provided at approximately 4 hours post dose, a standardized evening meal at approximately 10 hours post dose and a standardized evening snack at approximately 14 hours post dose. The percentage of food consumed and timing of meals will be recorded for all Day meals. Meals will be provided to participants at standardized times on non-dosing days.

6.3.2 Other Dietary Restrictions

- Participants are not permitted to consume any nutrients known to modulate cytochrome p-450
 (CYP) enzyme activity (eg, grapefruit or grapefruit juice, pomelo juice, star fruit, or Seville
 [blood] orange products) from 48 hours prior to admission until after discharge from the
 clinical unit.
- Participants are not permitted to consume food containing poppy seeds for 48 hours prior to screening and for 48 hours prior to admission until after discharge from the clinical unit.

6.3.3 Caffeine. Alcohol and Tobacco

- During the study, participants will abstain from ingesting caffeine- or xanthine-containing products (eg, coffee, tea, cola drinks, and chocolate) for 24 hours prior to admission until discharge from the study.
- During the study, participants will abstain from alcohol for 24 hours prior to screening and the 24 hours prior to admission until discharge from the study.
- Participants are not permitted to smoke or use electronic cigarettes or any nicotine-containing products within 12 months prior to screening until discharge from the study.

6.3.4 Activity

- Participants are to refrain from strenuous exercise and contact sports from at least 72 hours before the screening visit and then from 72 hours prior to admission until discharge from the study.
- Must not donate blood or plasma (outside of this study), within 4 weeks of study enrollment throughout the study duration, and for at least 90 days following last dose of study medication

6.4 Screen Failures

Screen failures are defined as participants who consent to participate in the clinical study but who are not subsequently randomized in the study/included in the analysis population.

A minimal set of screen failure information is required to ensure transparent reporting of screen failure participants, to meet the Consolidated Standards of Reporting Trials (CONSORT) publishing requirements, as applicable, and to respond to queries from regulatory authorities. Minimal information includes date of consent, demography, screen failure details, eligibility criteria, and any serious AEs.

6.4.1 Retesting During Screening or Lead-in Period

Participant Re-enrollment: This study does not permit the re-enrollment of a participant who has discontinued the study as a pretreatment failure.

Retesting of laboratory parameters and/or other assessments within any single Screening will be permitted (in addition to any parameters that require a confirmatory value).

The most current result prior to randomization is the value by which study inclusion will be assessed, because it represents the participant's most current clinical state.

Laboratory parameters and/or assessments that are included in Table 2-1, Screening Procedural Outline, may be repeated in an effort to find all possible well-qualified participants. Consultation with the Medical Monitor may be needed to identify whether repeat testing of any particular parameter is clinically relevant.

6.4.2 Activity

- Participants are to refrain from strenuous exercise and contact sports from at least 72 hours before the screening visit and then from 72 hours prior to admission until discharge from the study.
- Must not donate blood or plasma (outside of this study), from screening throughout the study duration, and for at least 90 days following last dose of study medication

7 STUDY INTERVENTIONS AND CONCOMITANT THERAPY

Study intervention is defined as any investigational intervention(s), marketed product(s), placebo, procedure(s) or medical device intended to be administered to a study participant according to the study protocol.

Study intervention includes IP as indicated in Table 7.1-1.

An IP, also known as investigational medicinal product (IMP) in some regions, is defined a pharmaceutical form of an active substance or placebo being tested or used as a reference in a clinical study, including products already with a marketing authorization but used or assembled (formulated or packaged) differently from the authorized form, or used for an unauthorized indication, or when used to gain further information about the authorized form.

Other medications used as support or escape medication for preventative, diagnostic, or therapeutic reasons, as components of the standard of care for a given diagnosis, may be considered as IPs.

7.1 Study Interventions Administered

The selection and timing of dose for each participant is as follows:

Table 7.1-1: Study Interventions

Intervention Name	BMS-986177 oral solution mg	BMS-986177 SDD capsules, mg	[14C]BMS-986177 Solution for Infusion µg/mL (NMT kBq/ mL)
Dose Formulation	Solution	SDD Capsules	Solution for IV infusion
Unit Dose Strength(s)	8		μg/mL
Dosage Level(s)	mg dose	mg dose AND mg dose (as mg capsules)	μg dose
Route of Administration	Oral, fasted	Oral, fasted AND fed	IV infusion, fasted
Sourcing	Prepared by the trial site	Provided centrally by the Sponsor	Prepared by the trial site
Packaging and Labeling	The oral solution will be provided in bulk container. Each bulk container will be labeled as required per country requirement.	Study intervention will be provided in a bottle. Each bottle will be labeled as required per country requirement	Study intervention will be provided in a bulk container. Each bulk container will be labeled as required per country requirement

In the morning of Treatment Period, Day, after fasting for at least 10 hours, each participant will receive a oral dose of milvexian oral solution, which will be followed by appropriate rinses and additional water, for a total volume of 240 mL. The time of dose administration will be called "0" hour. At 1 hour post dose (approximately Tmax), participants will receive an IV microdose of [14C]milvexian solution for infusion over 15 minutes.

For IV dosing only: the IV dose will be infused over approximately 15 minutes. This infusion will be in the opposite arm being used for PK sampling.

To assess tolerability of the IV administration, the first participant will be dosed at least 30 minutes prior to dosing the second participant. All subsequent dosing of the IV formulation will be staggered by at least 15 minutes. To allow for potential interruptions and pump variations, up to a 20% difference in duration of the infusion will not be considered a protocol deviation provided the full planned dosed is administered as these minor discrepancies should not have a significant impact on the overall study objectives.

The planned infusion time will be 15 minutes; the actual infusion start and stop time will be recorded in the source.

• The infusion will finish within ± 3 minutes of the nominal time point

For Treatment Periods , in the morning on Day , after fasting for at least 10 hours or following a standardized high-fat meal, each participant will receive a oral dose of milvexian as SDD capsule(s).

At the time of dosing, 240 mL of water will be administered to the participant along with his/her oral dose of study intervention. The time of dose administration will be called "0" hour.

Restrictions related to food and fluid intake are described in Section 6.3.

7.3 Blinding

This is a randomized open-label study. It has been determined that blinding is not required to meet study objectives. Blinding procedures are not applicable and access to treatment assignment information is unrestricted.

7.4 Dosage Modification

Not applicable for this Phase 1 study.

7.5 Preparation/Handling/Storage/Accountability

The IP must be stored in a secure area according to local regulations. It is the responsibility of the investigator, or designee where permitted, to ensure that IP is only dispensed to study participants. The IP must be dispensed only from official study sites by authorized personnel according to local regulations.

The product storage manager should ensure that the study intervention is stored in accordance with the environmental conditions (temperature, light, and humidity) as determined by BMS. If

concerns regarding the quality or appearance of the study intervention arise, the study intervention should not be dispensed, and BMS should be contacted immediately.

Study intervention not supplied by BMS will be stored in accordance with the package insert.

IP documentation (whether supplied by BMS or not) must be maintained that includes all processes required to ensure the drug is accurately administered. This includes documentation of drug storage, administration and, as applicable, storage temperatures, reconstitution, and use of required processes (eg, required diluents, administration sets).

- The investigator or designee must confirm appropriate temperature conditions have been maintained during transit for all study intervention received and any discrepancies are reported and resolved before use of the study intervention.
- The investigator, institution, or the head of the medical institution (where applicable) is responsible for study intervention accountability, reconciliation, and record maintenance (ie, receipt, reconciliation, and final disposition records).
- Further guidance and information for the final disposition of unused study interventions are provided in the APPENDIX 2.

Storage facilities for controlled substances must be securely locked and substantially constructed, with restricted access to prevent theft or diversion, as applicable by local regulations.

